The Effect of Administering the Probiotic *Lactiplantibacillus plantarum* DAD-13 on Procalcitonin Levels, C-Reactive Protein, and Interleukin-6 in Sepsis Patients in the ICU of H. Adam Malik Hospital, Medan

NCT Number: Pending

Document Date: July 9, 2025

Study Protocol

Title: The Effect of Administering the Probiotic *Lactiplantibacillus plantarum* DAD-13 on Procalcitonin Levels, C-Reactive Protein, and Interleukin-6 in Sepsis Patients in the ICU of H. Adam Malik Hospital, Medan

NCT Number: Pending

Document Date: July 9, 2025

Background and Rationale: Sepsis is a life-threatening organ dysfunction caused by a dysregulated host response to infection. Dysbiosis and disruption of intestinal barrier function are critical components of sepsis pathophysiology. Probiotics may modulate inflammatory responses and restore gut microbiota balance. *L. plantarum* DAD-13, an Indonesian probiotic strain, has demonstrated immunomodulatory potential in preclinical studies. This study aims to evaluate the effect of *L. plantarum* DAD-13 on inflammatory markers and gastrointestinal outcomes in ICU patients with sepsis.

Study Objectives: Primary Objective:

- To assess the effect of *L. plantarum* DAD-13 on Procalcitonin (PCT), C-Reactive Protein (CRP), and Interleukin-6 (IL-6) levels.

Secondary Objective:

- To assess changes in defecation frequency and stool consistency.

Study Design:

- Type: Prospective, randomized, double-blind, placebo-controlled trial
- Sample size: 30 patients (15 per group)
- Duration: 4-day intervention period

Eligibility Criteria: Inclusion:

- Age 18–65 years
- Diagnosed with sepsis
- Admitted to ICU
- Receiving enteral nutrition

Exclusion:

- Known gastrointestinal disease
- Immunocompromised status
- Probiotic allergy
- Use of other probiotic products

Intervention:

- Experimental Group: 2 capsules/day of L. plantarum DAD-13 (Vipilac®)
- Control Group: 2 capsules/day of placebo (maltodextrin)
- Duration: 4 days

Endpoints:

- Primary: Change in serum PCT, CRP, and IL-6 from baseline to day 4
- Secondary: Frequency and consistency of defecation

Data Collection and Monitoring:

- Biomarkers (PCT, CRP, IL-6) measured at T0 (day 1) and T1 (day 4)
- Stool data collected daily
- Double-blind protocol maintained throughout study

Ethics: Approved by the Health Research Ethics Committee of Universitas Sumatera Utara. Informed consent obtained from all participants or legal representatives.

Statistical Analysis Plan (SAP)

Study Population:

- Intent-to-Treat (ITT): All randomized participants
- Per-Protocol (PP): Participants who completed the 4-day intervention

Descriptive Analysis:

- Means and standard deviations (SD) for continuous variables
- Frequencies and percentages for categorical variables

Comparative Analysis:

- Within-group (T0 vs T1): Wilcoxon Signed Rank Test (non-parametric)
- Between-group: Mann-Whitney U Test for biomarkers, Chi-square for defecation frequency/consistency
- Significance level: $p < 0.05$

Missing Data:

- Data imputed using last observation carried forward (LOCF) method for missing T1 values

Informed Consent Form (ICF)

Study Title: The Effect of Administering the Probiotic Lactiplantibacillus plantarum DAD-13 on PCT, CRP, and IL-6 in Sepsis Patients

Investigator: [name] [name] **Institution:** H. Adam Malik Hospital, Universitas Sumatera Utara **Contact:** [contact], [name]

Purpose: You are invited to participate in a clinical study evaluating the effects of a probiotic on inflammation and gut function in sepsis patients. Participation is voluntary.

Procedures:

- You will receive either probiotic capsules or placebo for 4 days
- Blood samples will be taken twice (day 1 and day 4)
- Stool consistency and frequency will be recorded

Risks and Benefits:

- Risks: Mild gastrointestinal discomfort, rare allergic reaction
- Benefits: Possible improvement in inflammation and gut function

Confidentiality: All data will be anonymized. Your name will not appear in any publication.

Voluntary Participation: You may withdraw from the study at any time without affecting your medical care.

Consent: By signing this form, you agree to participate in this study.

Participant Name: _____ Date: _____ Signature: _____

Witness Name: _____ Signature: _____

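### The secondary objective is change in stool pattern, but the endpoint names no baseline or time point and the one test assigned to stool neither measures change nor uses a baseline

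*Protocol*

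**What the plan says.** Under Study Objectives, the secondary objective is "To assess changes in defecation frequency and stool consistency". Under Endpoints, the matching line is "Secondary: Frequency and consistency of defecation". The line above it shows how the protocol writes a change endpoint when it has one: "Primary: Change in serum PCT, CRP, and IL-6 from baseline to day 4".

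Under Data Collection and Monitoring, T0 (day 1) and T1 (day 4) are introduced for the three biomarkers. Stool has one line: "Stool data collected daily". The start of collection and its order relative to the first capsule are not given. The intervention lasts 4 days.

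In the Statistical Analysis Plan section, Comparative Analysis gives "Between-group: Mann-Whitney U Test for biomarkers, Chi-square for defecation frequency/consistency". A separate line plans a Wilcoxon signed-rank test of T0 against T1 within each group, without naming the variables.

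**The concern.** An objective about change needs three things: a reference record, an endpoint built on it, and an analysis that uses it. For stool the protocol states none of them. A daily record on day 1 could cover hours before the first capsule, after it, or both, so it cannot be called a baseline until its timing is fixed.

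Two things are at stake. First, the report could describe its stool result as a change when the planned between-group test compares status. Second, the groups are small, so they may well differ in stool pattern at entry by chance, and the chi-square has no term to take that into account. A usable baseline may be hard to recover once dosing has begun, so the point matters before enrolment.

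**Working it through.** **Does the plan carry change through?**

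| Element | Biomarkers | Stool |
|---|---|---|
| Objective | effect on levels | changes |
| Endpoint | change, baseline to day 4 | frequency and consistency, no time point |
| Baseline | T0, day 1 | none defined |
| Between-group test | Mann-Whitney U | chi-square, no day, no baseline term |
| Within-group test | Wilcoxon, T0 against T1 | not stated whether it applies |

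The word "changes" appears for stool only in the objective.

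**How large can chance imbalance be?** The document gives 15 per group and no stool rates, power or effect size, so it has no figure of its own to reproduce. The prevalence p of abnormal stool at entry is an assumption. With X1 and X2 independent Binomial(15, p), sum P(X1 = a)·P(X2 = b) over all pairs with |a − b| ≥ t. Three patients of 15 is 20 percentage points; four is 26.7.

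| p (assumed) | P(differ by ≥ 3) | P(differ by ≥ 4) |
|---|---|---|
| 0.20 | 0.249 | 0.107 |
| 0.30 | 0.318 | 0.161 |
| 0.40 | 0.351 | 0.191 |
| 0.50 | 0.362 | 0.200 |

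**What would a baseline buy?** As a rough guide, treat stool as a continuous measure with SD 1, a true effect of 0.8 SD, two-sided alpha 0.05 and baseline to follow-up correlation r. All of these are assumptions except the 0.05 level, whose sidedness the document does not state. The variance of the arm comparison relative to follow-up status alone is:

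- baseline as covariate: 1 − r²
- raw change score: 2(1 − r)

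With v this ratio, power ≈ Φ(0.8 / √(v × 2/15) − 1.96). For status alone v = 1: √(2/15) = 0.365, 0.8/0.365 = 2.19, 2.19 − 1.96 = 0.23, and Φ(0.23) = 0.59.

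| r (assumed) | v, covariate | Power, covariate | v, change score | Power, change score | Power, status |
|---|---|---|---|---|---|
| 0.3 | 0.91 | 0.63 | 1.40 | 0.46 | 0.59 |
| 0.5 | 0.75 | 0.72 | 1.00 | 0.59 | 0.59 |
| 0.7 | 0.51 | 0.87 | 0.60 | 0.81 | 0.59 |

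Under these assumptions the covariate analysis beats status alone at every correlation shown. The change score gains nothing at r = 0.5 and loses power below it.

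**The case against.** A reader might infer that no pre-treatment stool record is planned. The document does not say so. Day 1 is the baseline day for the biomarkers, and daily stool collection may well include it. What can be said is that no stool record is defined as pre-treatment.

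A reader might also infer that the objective cannot be answered. That goes too far. The within-group Wilcoxon line does not exclude stool, and daily data would let a day 1 to day 4 change be described. Neither route repairs the mismatch: if the Wilcoxon line does cover stool, it compares an untimed day-1 record with day 4 inside each arm, and that is not a comparison of change between arms.

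The strongest objection is that randomisation already makes a comparison of follow-up status valid. Chance imbalance is allowed for in the test's type I error, and any randomised trial analysed without covariates could be criticised in the same way. This stands in full: the imbalance figures show no bias and no error in the test, only the precision and clarity given up.

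It is also fair that the prevalences, correlations and effect size have no source in the document, and that the variance formulas belong to a linear model for a continuous outcome. They do not carry over exactly to ordinal or count models, so they are illustrative.

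**Conclusion.** The mismatch stands on the text alone. The objective is about change, the stool endpoint is status with no baseline or time point, and the one test assigned to stool neither measures change nor adjusts for baseline. This rests on no assumption.

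The consequence is limited. The between-group comparison remains valid, but it does not match the stated objective and it leaves precision unused with 15 per arm. For scale, a baseline difference of 3 or more patients has probability 0.32 to 0.36 if 30% to 50% have abnormal stool at entry, and 0.25 at 20%. In the continuous approximation, adjustment at correlation 0.5 removes 25% of the variance and raises power from 0.59 to 0.72 for a 0.8 SD effect. These sizes depend wholly on the assumed inputs. The point concerns a secondary endpoint and is minor.

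**What to change.** 1. Define the T0 stool record as frequency and consistency before the first capsule, for example over the preceding 24 hours.
2. State the endpoint on a named day or over the treatment period, and word the objective to agree with it.
3. Replace the unadjusted chi-square with a between-arm comparison that has the T0 value as covariate: an ordinal model for consistency and a count model for frequency. Do not use a raw change score.
4. State whether the within-group T0 against T1 line covers stool.
5. If no record before the first capsule can be taken, reword the objective to a between-group comparison of on-treatment stool frequency and consistency, and make no claim of change.

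The cost is one extra line on the case report form and matching edits to the objective, endpoint and analysis text. The downside is that the prior 24 hours may be incompletely documented for some patients.

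### Three unranked primary biomarkers are each tested at p < 0.05 with no rule for primary success; if any one may count, the false-positive rate is about 8–13% (assuming marker correlations of 0.9 to 0)

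*Protocol*

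**What the plan says.** Under Study Objectives, the single primary objective is to assess the product's effect "on Procalcitonin (PCT), C-Reactive Protein (CRP), and Interleukin-6 (IL-6) levels". Under Endpoints, the same three markers share one line: "Primary: Change in serum PCT, CRP, and IL-6 from baseline to day 4". Neither place names a lead marker. Study Design gives "Sample size: 30 patients (15 per group"), with no effect size, standard deviation or power.

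The document's section headed Statistical Analysis Plan (SAP) fixes the tests under Comparative Analysis. Between groups it reads: "Between-group: Mann-Whitney U Test for biomarkers, Chi-square for defecation frequency/consistency". Within groups it reads: "Within-group (T0 vs T1): Wilcoxon Signed Rank Test (non-parametric"). One threshold is stated for all tests: "Significance level: $p < 0.05". The section contains no success rule, testing order, composite or multiplicity adjustment, and does not say whether tests are one- or two-sided.

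**The concern.** Three primary tests at 0.05 can support at least three different decision rules: success if any marker is significant, success if one named marker is, or success only if all are. The first exceeds a 5% error rate for the primary objective, and the last stays within it at the price of power. The text neither states nor excludes any of them, so the choice stays open until the p-values are known.

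The practical consequence is a split result, with one or two markers of three significant. A reader holding only this document could not say whether the primary objective had been met, and nothing would stop the trial from being reported as positive on whichever marker succeeded.

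**Working it through.** **Inputs from the document:** three primary markers (Endpoints); 15 per arm, where 2 × 15 = 30 agrees with the stated total (Study Design); Mann-Whitney at 0.05 (Comparative Analysis). The choice of 30 cannot be reproduced, because no effect size, SD or power is given.

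**Assumptions, because the document is silent:** two-sided tests; one between-group test per marker; normally distributed changes with a common correlation between markers of 0 to 0.9; effects of 0.6 to 1.2 SD for power.

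**1. Simple limits for an any-one rule.** If each test had exactly 5% size and the markers were independent, 1 − 0.95³ = 14.3%. The bound at any correlation is 3 × 0.05 = 15%.

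**2. Actual size of the test.** The 15-versus-15 Mann-Whitney statistic is discrete. The exact two-sided test rejects at U ≤ 64 (and symmetrically), with size 4.53%. The normal approximation with continuity correction has mean 15 × 15/2 = 112.5 and SD √(15 × 15 × 31/12) = 24.1. U = 64 gives z = (112.5 − 64 − 0.5)/24.1 = 1.99, which rejects. U = 65 gives 47/24.1 = 1.95, which does not. The two versions therefore have the same rejection region. With independent markers the any-one error is 1 − (1 − 0.0453)³ = 13.0%.

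**3. Correlated markers, none affected.** Simulation, 100,000 trials per row:

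| Correlation | Any one p < 0.05 | All three p < 0.05 | Holm, family-wise |
|---|---|---|---|
| 0 | 13.2% | 0.01% | 4.3% |
| 0.3 | 12.5% | 0.05% | 4.2% |
| 0.5 | 11.6% | 0.21% | 4.1% |
| 0.7 | 10.3% | 0.65% | 3.5% |
| 0.9 | 8.0% | 1.8% | 2.8% |

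**4. Worst case for the all-three rule.** A false all-three claim requires every unaffected marker to reach significance, so its error cannot exceed the size of one test. With two markers truly affected and one not, the simulated error is 2.2–2.5% at a 1.0 SD effect and about 4.5% at 2 SD or more.

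**5. Power.** Ranges run over correlations 0 to 0.9:

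| Assumed effect | One marker, unadjusted | All-three rule, all affected | Holm per marker, all affected | Holm per marker, only that one affected |
|---|---|---|---|---|
| 0.6 SD | 32% | 3–22% | 20–22% | 18% |
| 0.8 SD | 52% | 14–40% | 39–40% | 34% |
| 1.0 SD | 71–72% | 37–61% | 60–62% | 53–54% |
| 1.2 SD | 86% | 64–79% | 78–82% | 72–73% |

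If only one marker responds, at 1.0 SD, the all-three rule succeeds in 0.2–1.2% of trials.

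**6. How often the result would be split.** This is P(any) minus P(all) with a 1.0 SD effect on every marker. At correlation 0 it is 97.7% − 36.8% = 60.9%; at 0.5, 91.5% − 47.8% = 43.7%; at 0.9, 81.6% − 60.9% = 20.7%. Even when the product works on all three markers, between a fifth and three-fifths of trials would end with a result that the document cannot classify.

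**The case against.** The strongest reply is that this is an omission: a success rule and a multiplicity method usually belong in a full SAP, which may exist elsewhere. That would carry weight if the protocol were silent on analysis. It is not. Its own SAP section fixes the test and the threshold for three co-listed primary endpoints, and any longer plan would have to be reconciled with that text.

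A second reply is that a 30-patient, four-day biomarker trial can be read as asking three separate questions, each answered at its own 5%, so that family-wise control is a matter of preference. That reading is available, but the document does not adopt it. It states one primary objective covering all three markers, in a randomized, double-blind, placebo-controlled design, and does not call itself exploratory. If separate claims are intended, it should say so.

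Two qualifications stand. First, 8–13% is not a bound. It rests on assumed correlations, normality and two-sided testing; at exact 5% size it reaches 14.3% with independent markers and falls to 7.4% at correlation 0.95. Second, publishing all three p-values would let a reader apply Holm afterwards, which limits the harm but does not prevent the rule being chosen after the results are known.

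**Conclusion.** The concern holds. The document fixes an unadjusted 0.05 for three unranked primary markers without saying what counts as success. Under an any-one rule the false-positive rate is about 8–13% for correlations from 0.9 down to 0. Under an all-three rule it is at most 5%, with clearly lower power than a single marker.

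That the success rule is missing can be read directly from the text and needs no assumption. The sizes depend on the assumed correlations, effects and sidedness. The six within-group tests (three markers × two arms) are not counted in the 8–13%. This should be fixed; it does not invalidate the design.

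**What to change.** State the primary success rule in the analysis section before unblinding. A workable text: the changes in PCT, CRP and IL-6 are compared between groups by two-sided Mann-Whitney tests, with Holm's procedure across the three at a family-wise 0.05; a primary claim is made only for markers significant after adjustment; within-group Wilcoxon tests are descriptive and support no claim of treatment effect. Under Holm the smallest p-value is compared with 0.05/3 = 0.0167, the next with 0.025 and the last with 0.05, stopping at the first failure.

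Alternatively, the sponsor may pre-name one primary marker, a fixed testing order, or an all-three rule with each test at 0.05, giving its grounds.

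Any of these takes one or two sentences and no new data. The costs differ:

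- **Holm:** at an assumed 1.0 SD effect, per-marker power drops from about 72% to 60–62% if all three markers respond, or to about 54% if only one does.
- **All-three:** power is 37–61% at the same effect on every marker, and close to nil if only one responds.
- **Fixed order:** later markers lose confirmatory status once an earlier one fails.
- **Single primary:** the other two markers become secondary.

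### Do the within-arm Wilcoxon tests, listed beside an unranked Mann-Whitney test, leave the placebo-controlled question undecided?

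*Protocol*

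**What the plan says.** The Study Design section describes a "Prospective, randomized, double-blind, placebo-controlled trial" with "Sample size: 30 patients (15 per group"). The Endpoints section gives "Primary: Change in serum PCT, CRP, and IL-6 from baseline to day 4". Data Collection and Monitoring defines the markers and time points: "Biomarkers (PCT, CRP, IL-6) measured at T0 (day 1) and T1 (day 4").

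The Comparative Analysis part of the SAP section has two test lines. The first is "Within-group (T0 vs T1): Wilcoxon Signed Rank Test (non-parametric"). The second is "Between-group: Mann-Whitney U Test for biomarkers, Chi-square for defecation frequency/consistency". A single 0.05 significance level follows and covers both. Under Missing Data, the rule is "Data imputed using last observation carried forward (LOCF) method for missing T1 values".

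No sentence ranks one test line above the other. None says whether the Mann-Whitney test takes the change from T0 to T1 or the T1 value.

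**The concern.** The primary endpoint is a change over time, and the only line that mentions T0 and T1 is the within-arm one. It comes first, under a heading about comparison, at the same significance level as the randomised test. A reader could take the Wilcoxon tests to be the analysis of the primary endpoint.

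That would be a serious mistake. In treated ICU patients with sepsis, inflammatory markers may fall between day 1 and day 4 because of ICU treatment, the natural course of the illness or regression to the mean. A within-arm test cannot separate these from a probiotic effect; the placebo arm exists to do that. A significant fall on probiotic, or a fall that is significant on probiotic but not on placebo, could then be reported as a planned result on the primary endpoint although neither uses the randomised comparison.

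**Working it through.** **Step 1: what each line fixes.**

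| Item | Within-arm line | Between-group line |
|---|---|---|
| Test | Wilcoxon signed rank | Mann-Whitney U |
| Variables | not named | the biomarkers, defined elsewhere in the Protocol as PCT, CRP and IL-6 |
| Time points | T0 against T1 | not stated (change or T1) |
| Uses randomisation | no | yes |

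Each line is abbreviated in a different place. Neither contradicts the endpoint. The Endpoints section supplies what the Mann-Whitney line omits, namely change from baseline to day 4.

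**Step 2: size of the error if efficacy were read within arms.** The Protocol gives 15 per arm, the 0.05 level and LOCF. It gives no expected fall, SD, T0-T1 correlation or missing rate, so those are assumptions. There is no power statement to reproduce.

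Setting: 40,000 simulated trials per row, one marker, normal change scores with SD 1, the same fall in both arms, and therefore no true effect. The signed-rank test rejects at W ≤ 25 or W ≥ 95 (exact two-sided size 4.8%). The Mann-Whitney test rejects at U ≤ 64 or U ≥ 161 (exact size 4.5%).

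| Shared fall (SD) | Probiotic arm significant | Significant on probiotic only |
|---|---|---|
| 0 | 4.9% | 4.7% |
| 0.3 | 18.1% | 14.8% |
| 0.55 | 48.6% | 25.2% |
| 0.8 | 80.1% | 16.1% |
| 1.0 | 93.8% | 5.9% |

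Mann-Whitney on change gives 4.4% to 4.7% throughout.

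The last column can be checked by hand. The arms are independent and identically distributed here, so if p is the chance of significance in one arm, the chance of probiotic only is p(1 − p):

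- At 0.55 SD: 0.486 × 0.514 = 0.250.
- At 1 SD: 0.938 × 0.062 = 0.058.
- The maximum is 0.5 × 0.5 = 0.25, so about 25% per marker is a ceiling whatever fall is assumed.

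**Step 3: does the open choice of variable harm the planned between-group test?** With log-normal markers (log SD 1, T0-T1 correlation 0.5 or 0.8), a shared 30% fall makes the probiotic arm alone significant in 21% and 44% of trials. Mann-Whitney stays at 4.3% to 4.7%, both on change and on T1 values.

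With 15% of T1 values missing at random and replaced by T0 under LOCF, the probiotic arm alone is significant in about 5%, 41% and 88% of trials at falls of 0, 0.55 and 1 SD. Mann-Whitney on change stays at about 4.4% to 4.8%.

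**Step 4: reading the result.** The high within-arm rates are the power of a valid test to detect a real fall over time. They become false positives only if someone relabels that fall as a treatment effect. The randomised test that the plan prescribes holds its level in every setting tried.

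**The case for a change.** The best case for acting is that the Protocol carries its own SAP section, so this cannot simply be put down to detail held elsewhere. That section places uncontrolled tests beside the controlled one without ranking them. At a shared fall of 0.55 SD, about 23% of trials with no true effect would show significance on probiotic only while the Mann-Whitney test is not significant. Two planned analyses would then point in different directions, and one added sentence, costing nothing in patients or data, would settle which counts.

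Much of this stands as description. The within-arm tests cannot answer the objective, the two lines are not ranked, and the form of the Mann-Whitney variable is left open.

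What does not stand is the step from there to a fault in the plan. Describing change within each arm alongside a between-group test is common practice and is wrong only when the within-arm result carries the treatment claim. No passage gives it that role. The heading over both lines contrasts with the descriptive part of the section, and T0 against T1 is a comparison in the ordinary sense; the heading does not turn it into evidence against placebo. A sentence resting the conclusion on each biomarker's between-group test would also leave open how many of the three must be significant, so it would not fix the decision rule by itself.

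**Conclusion.** No change to the plan is needed on this point. Followed as written, the plan gives a valid randomised comparison of PCT, CRP and IL-6, with a false-positive rate of about 4.5% per marker (4.3% to 4.8% across the settings tried). Leaving change or T1 unstated does not alter that rate. It affects only how closely the test matches the stated endpoint, and the Endpoints section already answers that.

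The large figures (49% and 94% for the probiotic arm alone, up to 25% for probiotic only) depend on a later misreport that no passage prescribes. They also rest on assumed falls, SDs and correlations, so the rate for this trial is unknown. They are a reason to read the published report with care: the treatment conclusion should come from the between-group result, and the within-arm p-values should be taken as description.

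Two limits apply. The rates are per marker and say nothing about testing three markers together. The LOCF runs assume that missing values are unrelated to arm; missingness that differs between arms was not examined.

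### The only between-group biomarker test is an unadjusted Mann-Whitney test: valid, but it forgoes adjustment for the T0 value already collected, a cheap gain in precision whose size depends on the T0-T1 correlation

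*Protocol*

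**What the plan says.** The Endpoints section defines the primary outcome as "Primary: Change in serum PCT, CRP, and IL-6 from baseline to day 4". Data Collection and Monitoring has each marker measured twice, at T0 on day 1 and at T1 on day 4. Study Design sets 30 patients, 15 per arm.

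Under Comparative Analysis in the Statistical Analysis Plan section, the between-group rule is "Between-group: Mann-Whitney U Test for biomarkers, Chi-square for defecation frequency/consistency", judged at 0.05. No other comparison of the arms is named for the biomarkers. The rule does not say whether the test is run on T1 or on change, or whether change is absolute or relative. T0 also enters a Wilcoxon signed rank test within each arm, and the missing-data rule: "Data imputed using last observation carried forward (LOCF) method for missing T1 values". Neither of these adjusts the between-arm comparison for baseline.

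**The concern.** With 15 patients per arm, precision is the scarce resource. Each patient is due to have a T0 value, and T0 will predict T1 to some degree. A test on T1 alone ignores that information. A test on change imposes a slope of one on T0, which adds noise unless the correlation is high. Regression on T0 lets the data set the slope, and it costs no patients and no measurements. What is at stake is the width of the interval for each marker and, for larger effects, power.

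**Working it through.** **Inputs from the protocol:** 15 per arm; one T0 and one T1 value per marker; level 0.05, taken as two-sided. The protocol gives no power calculation, so there is no figure of its own to reproduce.

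**Assumptions:** log-normal markers with equal log-SD at T0 and T1; log correlation r of 0.3 to 0.8, with higher values shown as a limit; log-SD 1.0 to 1.5 for power.

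**Step 1: adjustment alone.** Variance of the between-arm difference on the log scale, relative to T1 alone:

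- T1 alone: 1
- log change: 2(1 - r)
- adjusted for log(T0): (1 - r²)(1 + 1/26), where 26 = 2 × 15 - 4 is the small-sample cost of estimating the slope

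Adjusted over change is therefore (1 + r)/2 × 27/26. The CI width ratio is its square root.

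| r | variance ratio | width ratio | narrowing |
|---|---|---|---|
| 0.3 | 0.65 × 27/26 = 0.675 | 0.82 | 18% |
| 0.5 | 0.75 × 27/26 = 0.779 | 0.88 | 12% |
| 0.7 | 0.85 × 27/26 = 0.883 | 0.94 | 6% |
| 0.8 | 0.90 × 27/26 = 0.935 | 0.97 | 3% |
| 0.9 | 0.95 × 27/26 = 0.987 | 0.99 | under 1% |

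The ratio reaches 1 where 1 + r = 52/27, that is r = 0.93; above that, adjustment costs slightly more than it saves. In sample size, adjustment alone is worth 15/0.675 = 22, 15/0.779 = 19, 15/0.883 = 17 and 15/0.935 = 16 patients per arm at r 0.3, 0.5, 0.7 and 0.8. Simulation gives the same 18, 12, 6 and 3%.

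**Step 2: replacing the rank method.** On exactly log-normal data, an unadjusted t interval on log change is already about 5% narrower than the Hodges-Lehmann interval that belongs to the Mann-Whitney test, at every r. Combined: 0.82 × 0.95 = 0.78, 0.88 × 0.95 = 0.84, 0.94 × 0.95 = 0.89, 0.97 × 0.95 = 0.92. Simulated ratios are 0.78, 0.84, 0.90 and 0.92, a total narrowing of 8 to 22%.

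**Step 3: if the test is run on T1 alone.** The width ratio is the square root of (1 - r²) × 27/26, times 0.95: 0.92, 0.84, 0.69 and 0.58. The simulated total narrowing is 7, 16, 31 and 42% at r 0.3, 0.5, 0.7 and 0.8, in agreement to within a point.

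**Step 4: power (simulated, log-SD 1.0).** Mann-Whitney on log change / log-ANCOVA / rank ANCOVA, in %:

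| r | day-4 ratio 0.4 | day-4 ratio 0.7 |
|---|---|---|
| 0.3 | 50 / 70 / 68 | 11 / 17 / 16 |
| 0.5 | 64 / 79 / 75 | 14 / 18 / 17 |
| 0.7 | 85 / 91 / 88 | 21 / 26 / 23 |
| 0.8 | 96 / 98 / 95 | 29 / 34 / 30 |

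Rank ANCOVA keeps most of the gain at low r and almost none at 0.8, which fits steps 1 and 2. Mann-Whitney on T1 alone has 63-64% power at ratio 0.4 for every r. Power on absolute change depends on how far both arms fall together (20 to 62% at ratio 0.4, r 0.5, over the falls tried), so no single figure is given for it.

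**Step 5: checks.** Under no effect, rejection was 4.2 to 5.4% for every method. With heavy-tailed log values (t, 3 df), log-ANCOVA ran from 6 points below to 11 above Mann-Whitney on log change at ratio 0.4, and from -5 to +5 points at 0.7; the CI width ratio was 0.84 to 1.05. With an assumed 20% of T1 missing and carried forward, the gain was 5-15 points at ratio 0.4 and 1-4 at 0.7.

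**The case against.** The strongest reply is that Mann-Whitney is a conventional choice that keeps its level in a 30-patient trial, and that preferring a log-scale model is a matter of taste resting on a distribution the protocol never describes. Much of this stands. The test is not wrong, every input to the gain is assumed, and under heavy tails the planned test can do better. What remains is that the plan fixes a comparison with no baseline adjustment although T0 is collected anyway. Rank ANCOVA recovers part of the gain at low to moderate r without relying on log-normality.

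Four stronger readings are tempting, and the documents do not support them.

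- **That the comparison is biased or invalid.** Randomisation protects it, and the simulated level is 4-5%.
- **That T0 is otherwise unused.** It enters the within-arm Wilcoxon test and the carried-forward values; the point concerns the between-arm comparison only.
- **That adjustment itself narrows the interval by 8-22%, worth about 17-24 patients per arm.** That total includes about 5% from assuming normality on the log scale. At r 0.8 this is more than half of the 8%.
- **That the unstated scale of change and the absence of an effect estimate and CI are defects in themselves.** A fuller analysis plan may supply them. Here they only support the point, since fixing the analysis settles them too.

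**Conclusion.** The point holds as one of efficiency. The planned between-arm comparison is valid but leaves baseline information unused. For log-normal markers at 15 per arm, adjustment for log(T0) narrows the interval by about 18% at r 0.3, falling to 3% at r 0.8 and to practically nothing from 0.9, relative to unadjusted log change. Against the planned test as a whole, the narrowing is 8-22% if it is run on log change and 7-42% if it is run on T1.

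For a strong effect (ratio 0.4) the power gain over log change is 2 to 20 points across log-SD 1.0 and 1.5. At ratio 0.7 it is about 2 to 6 points on the rounded figures, with power low either way, so the benefit there is mainly a tighter statement of which effects remain compatible with the data. At log-SD 1.0, r 0.5 and a true ratio of 0.7, a typical interval is 0.36 to 1.35 instead of 0.32 to 1.52. The protocol supplies none of the SDs, correlations, distributions or effects behind these figures. The change is worth making because it is cheap, and confidence in its exact size is moderate.

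**What to change.** Before unblinding, make the primary between-group analysis for each marker an ANCOVA of log(T1) on treatment and log(T0), reported as a geometric mean ratio with its 95% CI. With log(T0) in the model, the treatment coefficient is the same whether the outcome is log(T1) or log(T1/T0), so it still answers the change-from-baseline question, on a relative scale. Keep a rank-based sensitivity analysis: rank ANCOVA, or Mann-Whitney on log change with a Hodges-Lehmann estimate and CI. If absolute change is what is meant, say so and adjust for T0 on that scale.

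The cost is one degree of freedom, an assumption of approximate log-normality, an effect expressed as a ratio, and a stated rule for values below the quantification limit. No new data are needed. The change does not resolve the carried-forward imputation or the testing of three primary markers each at 0.05, which are separate matters.
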